In a single arm, NIH-funded pilot trial in the United States and China, we were able to obtain a sensitivity and specificity of 100 and 79% when the HRME was used in conjunction with Lugol's chromoendoscopy in high-risk subjects undergoing endoscopic screening or surveillance. The negative predictive value of the HRME was 97% which suggests that use of the HRME may significantly decrease the number of mucosal biopsies needed during endoscopic evaluation. Given Lugol's known high sensitivity but low specificity (95% and < 60%) this is promising as the HRME may significantly reduce the false positive rate of Lugol's chromoendoscopic screening, the current standard of care. Research subjects recruited at the Jilin site will also be asked to complete a brief survey about beliefs and attitudes about esophageal cancer and screening. It is important to understand factors affecting patient decisions about cancer screening to increase utilization of new technologies and ultimately improve early detection of esophageal cancer in this high-risk population.

Section D: Purpose and Objectives

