The overall objective of this multicenter trial is to determine whether use of a low-cost, high-resolution microendoscope during diagnostic upper endoscopy can improve the efficiency and accuracy of endoscopic screening for esophageal squamous cell neoplasia (ESCN). This is a trial of a novel technology, a miniaturized, low cost (<\$3,500) microscope device which can be used during upper endoscopy to image the gastrointestinal epithelium. This portable, battery-operated high-resolution microendoscope (HRME) was developed by our collaborators at Rice University and provides greater than 1000X magnified images of the esophageal mucosa. In a single-arm, pilot study of the device in an enriched population of 60 high-risk subjects in China and the US, we used the microendoscope during routine Lugol's chromoendoscopic screening to categorize areas of abnormality (unstained areas). The sensitivity /specificity for the device seen in this study were 100% and 79%-a significant improvement over the sensitivity/specificity of Lugol's chromoendoscopy which were 97% and 52%. Thus, our presumption is that HRME can enhance the specificity (and lower the false positive rate) of Lugol's. As part of a National Cancer Institute R01 supplement (Figure 1), we have enhanced the current HRME technology by introducing an automated, ergonomic, augmented reality platform. The augmented reality platform displays, in real-time, the microscopic image colocalized with the endoscopic image, potentially allowing more targeted biopsies/treatment and increased accuracy. Our central hypothesis is that our approach can improve the efficiency and clinical impact of endoscopic screening and surveillance of ESCN by providing *in-vivo* optical biopsies comparable to standard histology. Specifically, HRME will facilitate accurate, rapid real-time endoscopic screening by non-expert clinicians. We also hypothesize the HRME will provide additional, more accurate information regarding the presence of neoplasia that will impact upon the physician's decision to obtain a mucosal biopsy or perform endoscopic therapy (endoscopic mucosal resection or ablation). This could potentially minimize the number of unnecessary biopsies and enable the physician to perform endoscopic therapy at the time of the initial examination, rather than delaying endoscopic treatment to another procedure following pathologic confirmation of the initial biopsies. We will compare (1) the current endoscopic "standard of care" (white light endoscopy with Lugol's iodine), (2) HRME with subjective, human interpretation, and (3) augmented reality HRME (software, 'machine' interpretation). The addition of (3) is the basis for our revision R01 and this amended IRB. The accuracy, efficiency, clinical impact and cost-effectiveness of each approach in the diagnosis and management of ESCN will be determined in both the Chinese and US healthcare systems. Specific endpoints: 1. Efficiency: (a) Diagnostic Yield: The number of neoplastic biopsies/total number of biopsies obtained in patients who receive biopsies. (b) 'Patients saved': Number of patients who receive no biopsies (c) Procedure time: Total procedure time in each group 2. Clinical impact: Determine potential clinical impact of HRME by determining if use of the device (with both subjective and automated read) changes the decision to perform endoscopic therapy and perform, or not perform, a mucosal biopsy when compared to LC alone. 3. Prospectively compare the performance characteristics of HRME-LC to LC for the prediction of squamous esophageal neoplasia in flat mucosa and mucosal lesions using histopathology as the gold standard. (a) Determine the sensitivity, specificity, positive and negative predictive value for the identification of neoplasia on a per biopsy and per patient analysis. 4. Determine the cost-effectiveness of HRME-LC to LC alone for the endoscopic screening and surveillance of ESCN in the US and China.

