
Section E: Protocol Risks/Subjects

E1. Risk Category

Category 3: Research involving greater than minimal risk and no prospect of direct benefit to the individual subject, but likely to yield generalizable knowledge about the subject's disorder or condition.

E2. Subjects

Gender:

Both

Age:

Adult (18-64 yrs)

Ethnicity:

All Ethnicities

Primary Language:

Chinese, English, Spanish, Vietnamese

Groups to be recruited will include:

Patients

Which if any of the following vulnerable populations will be recruited as subjects?

Employees or lab personnel

Vulnerable populations require special protections. How will you obtain informed consent, protect subject confidentiality, and prevent undue coercion?

Among the HRME image analysis study, a small number of employees (current GI fellows) will be included in the novice endoscopist group. The PI and study staff will explain the study procedures verbally in addition to providing the letter describing the study with the PI contact info as part of the waiver for written documentation of informed consent. The staff will explain to the fellows that participation is voluntary, that their performance on the test will not affect their standing in their department, and that they are able to withdraw from the study at any time.

E3. Pregnant woman/fetus

Will pregnant women and/or fetuses (as described in 45 CFR 46 Subpart B) be enrolled in the research?

No

E4. Neonates

Will neonates of uncertain viability or nonviable neonates (as described in 45 CFR 46 Subpart B) be enrolled in the research?

No

E5. Children

Will children be enrolled in the research?

No

Section F: Design/Procedure

F1. Design

Select one category that most adequately describes your research:

t) Drug, Phase II, Multi Center

Discuss the research design including but not limited to such issues as: probability of group assignment, potential for subject to be randomized to placebo group, use of control subjects, etc.

The patient will be assigned to one of two groups: Group A: HRME-LC (HRME + Lugol's) or Group B (Lugol's alone). Randomization assignments (HRME-LC vs. LC) will be computer-generated with allocation concealment using sealed envelopes.

For the image analysis study, there is no randomization. All participants will complete the same study procedures.

Research subjects at the Jilin site will also be asked to complete a survey component addressing barriers to esophageal cancer screening.

Inclusion Criteria:

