Sample Size Calculation (This has NOT changed from original IRB): The sample sizes are calculated separately for the two risk groups (650 in surveillance group and 650 in screening group). Among the surveillance group, we want to test non-inferiority in sensitivity and superiority in specificity of LCE+HRME vs. LCE alone. The standard endoscopic evaluation using LCE has high sensitivity of about 95% but with low specificity at about 65%. Based on the preliminary data, we hypothesize that LCE+HRME has the sensitivity of at least 90% level, which is similar to that of LCE, but LCE+HRME would improve the specificity to 85%. With significance level of 0.05 and 80% power, we need 223 neoplastic patients and 65 benign patients in each arm (LCE and LCE+HRME) to conclude that LCE+HRME has similar sensitivity as LCE alone and had higher specificity than LCE alone. Hence, we need 446 neoplastic patients and 130 benign patients. The sample size calculation is based on the formula in Pepe (Chapter 8, The statistical Evaluation of Medical Tests for Classification and Prediction, 2003).

According to the preliminary results, greater than 80% patients in the surveillance group would have neoplasia. We anticipate the enrollment of total 650 patients in the surveillance group to ensure the accrual of 446 neoplastic patients and 130 benign patients.

In screening group, we will study the accuracy of LCE+HRME for the diagnosis of neoplasia, and test whether the negative predictive value (NPV) of LCE+HRME is higher than LCE alone. The NPV for using LCE alone is about 95%. We hypothesize that the NPV for LCE+HRME should be at least 99% to be useful. A sample of 300 per arm would provide 82.1% power for this hypothesis with a 5% type-I error. Assuming an 8% loss to follow-up or incomplete data, we need to recruit 325 subjects per arm in the screening population.

Power Calculation (Augmented Reality HRME Revision): We anticipate having at least 400-500 subjects remaining by the time the Augmented Reality HRME revision IRB is approved and funding from the NCI obtained. With 400 patient Augmented Reality HRME data, assuming an accuracy of 83% AND 650 LC patient, assuming an accuracy of 57%, the study should have >93% power to detect a statistically significant difference with an alpha error rate of 0.05.

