For the HRME image interpretation study, the sample size of 10 endoscopists was selected based on a prior power analysis based on non-inferiority. The 10 endoscopists will review about 140 HRME images. It is hypothesized that software interpretation of the HRME images will be non-inferior to the endoscopist interpretation. Non-inferiority is defined as a 10% difference in specificity between the two groups with 90% power and alpha of 0.05.

G2. Data Analysis

Provide a description of your plan for data analysis. State the types of comparisons you plan (e.g. comparison of means, comparison of proportions, regressions, analysis of variance). Which is the PRIMARY comparison/analysis? How will the analyses proposed relate to the primary purposes of your study?

Among the surveillance group, three analyses in testing the null hypotheses will be performed, including two interim analyses and one final analysis. The analysis will be performed when 220, 440 and 650 study subjects have been accrued, respectively.

The interim analysis will use a symmetric two sided group sequential design using a Hwang-Shih-DeCani spending function with beta spending of .4, which provides an O'Brien-Fleming-like conservative upper bound. This approach requires a two sided significance level of 0.0026 and 0.0114 for the interim analysis and 0.0464 for the final analysis of overall survival.

There will be no interim analysis for the screening population.

The primary analysis for the surveillance group is to test non-inferiority in sensitivity and superiority in specificity of LCE+HRME vs. LCE alone. The test statistic is based on the formula in Pepe (Chapter 8, The statistical Evaluation of Medical Tests for Classification and Prediction, 2003). Additionally, sensitivity and specificity of LCE+HRME vs. LCE alone will be estimated on a per patient basis with 95% confidence intervals. The primary goal for the screening group is to test whether the negative predictive value (NPV) of LCE+HRME is higher than LCE alone. This is done using Fisher's exact test. Additionally, the negative predictive value will be summarized with 95% confidence intervals.

The secondary analysis includes diagnostic yield, clinical efficiency, clinical impact, progression rate, and the rate of adverse events.

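### The screening group's 82.1% power counts all 300 patients per arm as test-negative; with the surveillance specificities borrowed, power is roughly 50–70%

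*Combined protocol and SAP*

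**What the plan says.** Section G1 sizes the screening group to show a higher NPV for LCE+HRME than for LCE alone. The comparator value is given as "The NPV for using LCE alone is about 95" per cent, and LCE+HRME is hypothesised to reach at least 99%. It then states: "A sample of 300 per arm would provide 82.1% power for this hypothesis with a 5% type-I error". The only further step is for missing data: "Assuming an 8% loss to follow-up or incomplete data, we need to recruit 325 subjects per arm in the screening population". Section G2 makes this comparison the primary goal for the screening group and names the test: "This is done using Fisher's exact test".

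No prevalence, sensitivity, specificity or expected test-negative fraction is given for screening. Lugol's accuracy appears elsewhere:

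- in G1, for surveillance: "The standard endoscopic evaluation using LCE has high sensitivity of about 95% but with low specificity at about 65" per cent, with LCE+HRME at 85% specificity and at least 90% sensitivity;
- in the background on the pilot trial: "Lugol's known high sensitivity but low specificity (95% and < 60" per cent;
- in Section D: "sensitivity/specificity of Lugol's chromoendoscopy which were 97% and 52" per cent.

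**The concern.** NPV is a proportion among patients whose test is negative. A sample size for comparing two NPVs is therefore a number of test-negatives per arm, and it must be converted to enrolled patients through the expected negative fraction. G1 makes a conversion of this kind for surveillance, where 446 neoplastic and 130 benign patients become 650 enrolled. For screening there is none: 300 becomes 325 for losses alone.

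The comparison is the primary goal for 650 of the 1,300 patients. If the denominators are much smaller than 300, the risk of missing a true 95%-to-99% difference is well above the 18% implied by the stated power, and a non-significant result would be read as stronger evidence than it is.

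**Working it through.** **1. Reproducing 82.1%.** Among test-negatives, the false-negative proportions are 0.05 (LCE) and 0.01 (LCE+HRME). With 300 per arm and two-sided alpha 0.05:

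- pooled proportion 0.03; standard error under the null √(0.03 × 0.97 × 2/300) = 0.01393;
- standard error under the alternative √(0.05 × 0.95/300 + 0.01 × 0.99/300) = 0.01383;
- power = Φ[(0.04 − 1.96 × 0.01393)/0.01383] = Φ(0.918) = 82.07%.

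Other methods at 300 per arm do not match: unpooled 82.4%, continuity-corrected 75.1%, arcsine 86.7%, one-sided pooled 89.2%. The planned two-sided Fisher test, by exact enumeration, gives 79.8%.

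**2. What 300 counts.** 325 × 0.92 = 299, so 300 is evaluable patients per arm, all of them placed in the NPV denominator.

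**3. Why that contradicts the hypothesis.** If every patient in both arms tested negative, NPV would be 1 − prevalence in each arm. Section F1 randomises ("Randomization assignments (HRME-LC vs. LC) will be computer-generated with allocation concealment using sealed envelopes"), so expected prevalence is the same in both arms, and 95% against 99% could not arise. This step needs no borrowed value.

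At one common prevalence, the largest z-test power for 95% against 99% under any accuracy is 81.1%. It occurs at 5% prevalence with 300 and 287.9 negatives, and requires an LCE sensitivity of zero.

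**4. Power on test-negatives.** True negatives = 300 × specificity × (1 − prevalence), so

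negatives per arm = 300 × specificity × (1 − prevalence) / NPV.

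*Assumption:* specificities of 65% (LCE) and 85% (LCE+HRME) are borrowed from surveillance, and the NPVs are held at 95% and 99%. LCE sensitivity is then a residual: 1 − negatives × 0.05 / (300 × prevalence).

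| Prevalence | Negatives, LCE / LCE+HRME | z-test power | Fisher power | Implied LCE sensitivity |
|---|---|---|---|---|
| 40.6% | 122 / 153 | 51.7% | 46.7% | 95% |
| 20% | 164 / 206 | 63.5% | 60.4% | 86% |
| 7.9% | 189 / 237 | 69.2% | 67.4% | 60% |
| 3.3% | 198 / 249 | 71.2% | 69.5% | 0% |

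Prevalence of 40.6% is where LCE at 95%/65% has an NPV of 95%. Prevalence of 7.9% is where LCE+HRME at 90%/85% has an NPV of 99%. Prevalence of 3.3% is the lowest at which LCE can have an NPV of 95% with 65% specificity: odds 0.65 × 0.05/0.95 = 0.0342.

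**5. Other specificities** (z-test / Fisher).

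- LCE 60% (the top of the background's range) and HRME 79% (pilot): 68.3% / 68.9% at the lowest feasible prevalence, 3.1%; 50.2% / 47.6% at 38.7%, where LCE sensitivity is 95%.
- Pilot values 52% and 79%, prevalence 5–40%: 48–65% / 43–62%.
- LCE 65% and LCE+HRME 100%: 198/293 negatives, about 75% by either test.
- Outside the documents, 90% and 95% at 5% prevalence: 270/273 negatives, 78.2% / 80.5%, with an implied LCE sensitivity of 10%.

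**6. Why the surveillance values cannot be carried over as a set.** False negatives per true negative, per unit of disease odds, are 0.05/0.65 = 0.077 for LCE and 0.10/0.85 = 0.118 for LCE+HRME. At those values LCE+HRME has the lower NPV at every prevalence: 99.0% against 99.3% at 7.9%, and 92.6% against 95.0% at 40.6%.

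**The case against.** The denominator point is hard to dispute; the case against is about size and remedy.

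- **Implied sensitivities.** Fixing the NPVs and borrowing only specificities forces LCE sensitivity down to 86%, 60% or 0% in three of the four rows, while the documents give 95–97%. Only the 40.6% row keeps 95%, and nothing in the documents supports that prevalence for screening. This stands as a caution: the range is an illustration. It does not rescue the stated figure, because the row that respects the documents' sensitivity has the lowest power.
- **Source of the specificities.** They come from a surveillance group with more than 80% neoplasia and from an enriched pilot of 60 patients, possibly analysed per area. Screening specificity may be higher. That is fair, but the plan states none.
- **A floor read as a point value.** LCE+HRME sensitivity is put at 90% or more. Above 1 − 0.85 × 0.05/0.65 = 93.5%, with 85% specificity, its NPV exceeds that of LCE at 95%/65%. This is correct, so step 6 applies to 90%/85% as stated. Yet with LCE at 95%/65%, an NPV of 95% again requires 40.6% prevalence, and holding LCE+HRME at 99% there gives the 52% row.
- **Verification.** F2 biopsies only Lugol's-abnormal areas, so some test-negative patients may have no histology, and a negative LCE result per patient is not clearly defined. This is a separate matter, and missing verification could only shrink the denominators further.
- **Consequence.** G2 requires 95% confidence intervals, which would show imprecision. They do not correct the stated power.

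**Conclusion.** The concern holds. The 82.1% is the power for 300 test-negative patients per arm, whereas the plan provides 300 evaluable patients per arm. This conclusion rests on the documents alone. The figure is also not the power of the planned Fisher test.

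The size of the shortfall is conditional. With the surveillance specificities borrowed and the NPVs held as stated, power is roughly 50–70% and the type II error roughly 30–50%, against 18% as implied. With LCE specificity at 65% or lower, power is at most about 75% even if LCE+HRME had perfect specificity. Every case examined falls below 82.1%. The documents do not allow a single replacement figure.

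**What to change.** Delete 82.1% from G1. State the screening prevalence, and the sensitivity and specificity in each arm, that together yield NPVs of 95% and 99% at one common prevalence. Compute the expected test-negatives per arm among 300 evaluable patients by the formula in step 4, and report the power of Fisher's exact test on those counts. The surveillance values 95%/65% and 90%/85% cannot serve as that set. The sponsor must supply the screening assumptions, so no replacement power is proposed here.

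The cost is text in G1: no extra patients, procedures or data. The downside is that, unless other screening assumptions can be justified, the restated power will probably fall below 80%, and the plan will have to say so.

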All-inclusive outpatients undergoing routine (standard of care) Lugol's chromoendoscopic evaluation for suspected or known squamous cell neoplasia will be enrolled as well as any outpatients referred to the clinic with any prior history of squamous cell dysplasia and/or neoplasia will also be considered eligible as they will serve as study population for the surveillance group. Patients seen in outpatient clinics who are high risk for esophageal dysplasia/neoplasia, including patients with known history of head/neck cancer or of Northern Chinese descent will also be eligible for enrollment.

Six novice and four expert endoscopists will be the research subjects for the post hoc image analysis project. The subjects will be practicing endoscopists or GI fellows at current study sites or other institutions.

Exclusion Criteria:

- Allergy or prior reaction to the fluorescent contrast agent proflavine - Patients who are unable to give informed consent - known advanced squamous cell carcinoma of the distal esophagus, or dysplastic/suspected malignant esophageal lesion greater than or equal to 2cm in size not amenable to endoscopic therapy - Patient unable to undergo routine endoscopy with biopsy: - women who are pregnant or breastfeeding - prothrombin time greater than 50% of control; PTT greater than 50 sec, or INR greater than 2.0 - inability to tolerate sedated upper endoscopy due to cardio-pulmonary instability or other significant medical issues

F2. Procedure

Written informed consent will be obtained prior to study participation using the IRB-approved consent form.

The patient will be assigned to one of two groups: Group A: HRME-LC (HRME + Lugol's) or Group B (Lugol's alone). Randomization assignments (HRME-LC vs. LC) will be computer-generated with allocation concealment using sealed envelopes. As part of the NCI R01 supplement, the HRME-LC arm will now include the augmented reality HRME component following the standard HRME image. The Augmented Reality (AR) glasses will allow the endoscopist to see the microendoscopic (HRME) and endoscopic image at the same time. We now can produce a colocalized image that can be seen on the glasses at the same time as the endoscopic image AND in the same field of view. This does NOT change patient care. Rather, it improves the visualization of the endoscopist as shown in Figure 1.

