Separately, 10 endoscopists (6 novice and 4 expert) will be asked to interpret a selection of the HRME images. The novices will include current GI fellows at BCM and novice endoscopists on the protocol, while the expert endoscopists will be experienced endoscopists listed on the protocol. The 10 subjects will receive information about the procedures verbally as a waiver of documentation of consent is requested. Each of the subjects will first receive training using a training set, and then will be evaluated using a testing set of images. They will be asked to give a read (neoplastic or non-neoplastic) and then to provide their confidence level (high or low) for each image determination. Following the subjective HRME image read, each image will be evaluated using the automated software algorithm, with the subjective and automated reads being blinded to each other, as well as to the gold standard consensus pathology read by 2 expert GI pathologists. The subjective reads will be compared to the automated reads and the consensus pathology reads.

Subjects at the Jilin site will be asked to complete a survey addressing barriers to esophageal cancer screenings. Subjects will be asked about beliefs and attitudes surrounding screening techniques.

Section G: Sample Size/Data Analysis

G1. Sample Size

How many subjects (or specimens, or charts) will be used in this study?

Local: 300 Worldwide: 1300

Please indicate why you chose the sample size proposed:

This is an IRB revision and will NOT change our proposed sample size. Rather, in the remaining patients to be accrued, we will determine the accuracy of our revised (AR platform). Thus, the goals and sample size of the original trial will remain intact which is to compare LCE to LCE+HRME (subjective read).

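### The AR power statement counts 400 AR patients where the stated minimum gives about 200-250 (if both arms, 1:1), and part of its 650-patient LC comparator pre-dates AR

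*Combined protocol and SAP*

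**What the plan says.** G1 (Sample Size) says the revision leaves the total of 1300 unchanged and that "in the remaining patients to be accrued, we will determine the accuracy of our revised (AR platform" will be determined. The AR power paragraph then gives the expected number: "We anticipate having at least 400-500 subjects remaining by the time the Augmented Reality HRME revision IRB is approved". The calculation itself follows: "With 400 patient Augmented Reality HRME data, assuming an accuracy of 83% AND 650 LC patient, assuming an accuracy of 57" per cent, with more than 93% power at an alpha of 0.05.

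F2 (Procedure) confines AR to one arm: "the HRME-LC arm will now include the augmented reality HRME component following the standard HRME image".

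No allocation ratio is written. The sample size text in G1 uses equal arms throughout. Surveillance needs "223 neoplastic patients and 65 benign patients in each arm", doubled to 446 and 130. For screening, "we need to recruit 325 subjects per arm in the screening population". The risk groups are "650 in surveillance group and 650 in screening group".

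G2 (Data Analysis) tests LCE+HRME against LCE for sensitivity and specificity (surveillance) and NPV (screening), and G1 ties those goals to the subjective read. Section D includes the automated read in the clinical impact objective. G2 names no accuracy test of AR against LC within the trial.

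**The concern.** Two things do not fit together. First, a pool of 400-500 patients shared between two arms cannot supply 400 patients to one of them at 1:1. Second, 650 is exactly half of 1300, so the LC figure is the full-trial arm, including patients enrolled before AR existed in the trial.

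Randomization protects a comparison of AR patients with LC patients randomized over the same period. It does not protect the part of the contrast that sets AR patients against earlier LC patients, where changes over time in risk-group mix, operators or sites could enter. Because G2 does not name the AR accuracy analysis, its control group, unit and stratification would be open to choice after the data are seen.

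**Working it through.** **Inputs.** AR 400 at 83%; LC 650 at 57%; alpha 0.05; at least 400-500 remaining; total 1300 (all G1). AR in the HRME-LC arm only (F2). Assumed: two-sided test and 1:1 allocation.

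**The plan's figure.** Power = Φ[(|p1 − p2| − 1.96·SE0)/SE1], with SE0 pooled and SE1 unpooled.
- 400 vs 650: pooled p = (332 + 370.5)/1050 = 0.669; SE0 = 0.0299; SE1 = √(0.1411/400 + 0.2451/650) = 0.0270. Then (0.26 − 0.0586)/0.0270 ≈ 7.5, so power exceeds 99.99%.
- The statement of more than 93% is thus true as a bound, but 93% itself is not reproduced. These accuracies need only about 71 per arm for 93% power. The plan does not give the method behind the figure.

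**AR count, if the 400-500 is both arms.** 400/2 = 200; 500/2 = 250. To reach 400 AR patients: 400 × 2 = 800 remaining.

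**LC arm.** 1300/2 = 650, the whole arm. Share enrolled before AR:

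| Reading of 400-500 | Concurrent LC | Pre-AR LC | Share of 650 |
|---|---|---|---|
| Both arms | 200-250 | 450-400 | 69%-62% |
| HRME-LC arm alone | 400-500 | 250-150 | 38%-23% |

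**Power at the corrected counts (83% vs 57%).**
- 200 vs 200: SE0 = √(0.70 × 0.30 × 2/200) = 0.0458; SE1 = 0.0439; (0.26 − 0.0898)/0.0439 ≈ 3.87; power 0.9999.
- 250 vs 250 and 200 vs 650: above 0.9999.

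**Difference detectable with 93% power from an LC accuracy of 57%.** 10.6 points (400 vs 650), 13.4 (200 vs 650), 14.7 (250 vs 250), 16.3 (200 vs 200). All are well inside the planned 26 points.

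**Precision.** 95% half-width = 1.96·SE1: 5.3 points (400 vs 650), 6.4 (200 vs 650), 7.7 (250 vs 250), 8.6 (200 vs 200).

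**Concurrent LC data already collected.** F2 has every subject in both arms examined with Lugol's. The endoscopist's impression and plan are recorded for each Lugol's abnormal area, and all such areas are biopsied. In the HRME-LC arm the human read and then the machine read follow on the same sites, before biopsy. Each AR patient therefore carries a Lugol's impression and a machine read judged against the same histology.

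**The case against.** The strongest reply is that the design already holds concurrent Lugol's data. Because each AR patient has a Lugol's impression on the same biopsied sites, a within-patient comparison of AR with LC is available and would be unaffected by drift in case mix. This stands. A reader might infer that the trial has no protected AR comparison, or that only post-revision LC-arm patients can serve as controls; F2 does not support either. What is missing is a statement in G2 that the paired data will be used. The power sentence, with its 650 LC patients, most naturally describes the full LC arm instead.

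The count is also conditional. It needs 1:1 allocation, the both-arms reading of the remaining patients, and the floor of an at-least figure. If the 400-500 means the HRME-LC arm alone, 400 is right and a minority of the LC arm pre-dates AR. This also stands, so the first request is for clarification. Some LC patients still pre-date AR on either reading: with equal arms, 400 AR patients have about 400 concurrent LC-arm patients, not 650.

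Finally, no harm is demonstrated. The documents do not show that patient mix or Lugol's technique changes over time, and the same two pathologists read all specimens. That limits the weight of the point but does not remove the case for naming a concurrent comparison in advance.

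**Conclusion.** The point holds in a limited form. At the stated minimum, with both arms counted and 1:1 allocation, the AR number is overstated by a factor of 1.6 to 2 (400/250 to 400/200). Between 62% and 69% of the 650 LC patients would pre-date AR, or 23-38% on the alternative reading. The contrast that the power sentence implies is therefore partly non-concurrent, and G2 does not define another.

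A reader might infer from the smaller count that the AR comparison is underpowered. The plan's own accuracies do not support that: power stays above 99.9% at 200 vs 200. The original comparison of LCE with LCE+HRME (subjective read) is not affected. The correction is worth making because it is cheap and removes an avoidable source of bias. Confidence is moderate, since the allocation ratio and the scope of the 400-500 are inferred.

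**What to change.** **G1.** Say whether the 400-500 remaining patients are both arms together, and state the allocation ratio. If both arms, restate the AR and concurrent LC-arm numbers as about 200-250 each at the minimum, and recompute the power for those numbers with its method.

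**G2.** Add an AR accuracy analysis whose main comparison is concurrent. Choose one of:
- the machine read against the Lugol's impression in the same AR patients, on the same histology, by a paired method that allows for several sites per patient; or
- AR patients against LC-arm patients randomized after the revision, stratified by risk group.

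Use all 650 LC patients, also stratified, only as a sensitivity analysis. Define accuracy and its unit (per patient or per biopsy).

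**Cost.** Wording only, with no new patients or data. The stated sample becomes smaller. If the between-arm version is chosen, the 95% half-width is 7.7-8.6 points, against 6.4 for 200 vs 650. The precision of the paired version depends on how often the two reads disagree, which the documents do not give.
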